Mini International Neuropsychiatric Interview for the DSM-5 (MINI)(59): Structured interview to determine Axis I psychiatric conditions based on DSM-5 criteria.	Psychiatric History	х				
Patient Health Questionnaire Nine (PHQ9)(60): Self-Report measure of depressive symptoms.	Depressive Symptoms	х		х		
Time Line Follow Back (TLFB)(61) and Clinical Opioid Withdrawal Scale (COWS)(57): The TLFB is a validated measure quantifying drug use; average daily morphine equivalents will be calculated. The COWS is a validated measure quantifying withdrawal severity.	Opiate Use and Withdrawal	х				
Subjective Opioid Withdrawal Scale (SOWS) (68): The SOWS is a validated self-administered measure of opioid withdrawal.	Opiate Withdrawal	х	x			
The Barratt Impulsiveness Scale (BIS11) (69): The BIS is a validated questionnaire designed to assess the personality/behavioral construct of impulsivity.	Impulsivity	х				
The Pittsburgh Sleep Quality Index (PSQI) (70): Validated instrument used to measure the quality and patterns of sleep in adults.	Sleep	х		Х		
Work Productivity and Activity Impairment Questionnaire (71): The Work Productivity and Activity Impairment (WPAI) questionnaire is a well validated instrument to measure impairments in work and activities.	Functional Impairment	х		х		
The Rand 36 Item Short Form Health Survey (73): Validated self-report to assess quality of life.	Quality of Life	х		х		
Aim 1: Cue induced Craving: Primary ou paradigm.						
Prescription Opiate Craving Scale (21): Three item opiate craving scale. The three-item scale will also be administered at 1 and 4 week follow-	Provoked Opiate Craving	Х	X			

ups, but there will be no cue provocation.							
Aim 2: Pain Outcomes: Primary outcome: Change score in thermal pain threshold and pain tolerance.							
Mechanical, Thermal, and DNIC Pain Assessment: See description above.	Quantitative Sensory Assessment	x	x				
Brief Pain Inventory (23) and McGill Pain Questionnaire (24): Self report measures assessing severity, functional impairment, and affective components of pain. Administered daily during the acute phase of the study and at both follow-up visits.	Subjective Pain	х	x	x			
Exploratory Aims: Substance Use: Primary outcome: Abstinence over the final two weeks of the study, as defined by no self-reported use and a negative final urine drug screen. Executive function/inhibitory control: Will be measured using two validated computer tasks.							
Urine Drug Screen	Objective Substance Use	Х		x			

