Time Line Follow Back (61): See above.	Subjective Substance Use	х		x			
South Carolina Prescription Monitoring Program: Online database of all controlled substance prescriptions filled in the state of South Carolina.	Filled Prescription Opiates				х		
The "GoGo/NoGo" task: Participants are instructed to press a button in response to common (gray colored circles: 75% of trials) and rare (yellow colored circles: 12.5% of trials) Go stimuli and inhibit responding to rare NoGo stimuli (blue colored circles: 12.5% of trials). The task provides errors of omission and reaction times during Go trials, controls for novelty detection during processing of rare Go trials (yellow circles) and errors of commission on NoGo trials (blue circles).	Inhibitory Control						
Delayed Discounting Task: Participants will decide between a series of theoretical monetary rewards (exe: smaller rewards now, or larger rewards later) in a brief computerized task.	Delayed Discounting	х	x				

DATA MANAGEMENT AND STATISTICAL ANALYSIS: Data will be managed using REDCap. DATA MANAGEMENT AND STATISTICAL ANALYSIS: Data will be managed using REDCap. Randomization: Participants will be randomized to active or sham rTMS. Urn randomization will be used to ensure balance on three pre-specified covariates: depression status (HRSD at baseline ≥16 indicating moderate or greater depression), self-reported pain over the past three months, and planned use of replacement therapy following discharge. Statistical Analysis: Changes in study outcomes will be estimated and analyzed using several approaches. When parametric modeling assumptions can be made, changes over time will be compared between treatment groups (active rTMS vs. sham rTMS) using general linear mixed models (GLMMs). The

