GLMMs will allow us to estimate group-specific changes over time and overall effect sizes, along with the variation in those measures, while controlling for relevant baseline covariates (e.g. baseline craving, morphine equivalents, withdrawal). In an attempt to determine whether rTMS impacts craving and pain by reducing depressive symptoms, we will also examine models that do and do not control for changes in depression scores. Although we will likely not be powered to detect between-group differences in binary outcomes (i.e. drug use), such effects will be explored using generalized mixed models, and for time-to-event data (e.g. days to first opioid use), survival analysis models will be constructed. When parametric modeling assumptions do not appear to be valid, alternative (e.g. non-parametric) approaches will be used to estimate treatment efficacy and its precision. Primary outcomes will also be analyzed for evidence of differential treatment effects in subgroups determined by gender, race, and ethnicity. Post-hoc exploratory analyses using GLMMs within the active rTMS group will address whether specific characteristics (e.g. demographics, baseline craving, morphine equivalents, withdrawal) are associated with a better treatment effect. The subgroup-specific treatment effects and corresponding confidence intervals will be constructed and will be interpreted in terms of their clinical, rather than statistical, significance. Sample Size Justification: A total of n=40 participants (n=20 per arm) will be recruited. We anticipate that <20% of study participants will withdraw from the study or be lost to follow-up, meaning that ≥ n=32 participants are expected to complete the study. This sample size ensures that group-specific changes will be able to be estimated in a precise fashion, with 95% confidence intervals extending ~0.5 standard deviation units. Similarly, the overall effect size confidence interval will likely extend only 0.3 standard deviation units. As an exploratory and developmental R21 project, we recognize that our final sample size may not result in a fully powered study design. Nevertheless, our sample size will provide >80% power to detect large effect sizes (equivalent to a Cohen's d of 1.0), assuming 2-sided hypothesis testing and an alpha level of 0.05. Our preliminary work and work of others suggests that differences of this magnitude may be present within our proposed sample. For example, for Aim 1, recent investigations have found large effect sizes, with (20) reporting a d=0.84, and (18) reporting a d=0.98. For Aim 2, our recent single session study reported a d=0.65. Model based means and variability estimates will be derived from unadjusted and adjusted analyses and will be vital for designing a larger, more definitive trial in the context of a subsequent R01 submission. Relapse, Drop-Out and Clinical Deterioration: Every effort will be made to re-engage participants who miss appointments. Clinical deterioration, such as exacerbation of psychiatric or substance use disorder, will be assessed on a case-by-case basis and appropriate referral will be made. Participants will be considered drop outs if they do not come back for follow-up visits after three attempts to contact. With the exception of participants who formally withdraw from the study, we will attempt to assess early terminators at the time of discontinuation and at the post-treatment time points. These participants will be considered in the intent-to-treat efficacy analyses. Strategies to Ensure a Robust and Unbiased Approach: The proposed study will achieve robust and unbiased results via several design features including: explicit inclusion/exclusion criteria; randomization of treatment condition; the use of a validated sham control; use of validated laboratory and interview/self-report measures and methods; explicit hypotheses and corresponding planned statistical analyses; power estimates; planned handling of retention/attrition and missing data; and careful consideration of potential confounds. All experimental details are reported in a detailed manner to support replication. Consideration of gender as a biological variable: Though this trial is not powered to detect gender differences, we will perform our analysis using gender as a potential covariate. Should there be a potential gender difference found, we will use that data to power a larger trial

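### Comparing models with and without same-visit depression change cannot show whether rTMS acts on follow-up craving and pain through mood

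*Combined protocol and SAP*

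**What the plan says.** The Statistical Analysis text in section D states a causal purpose: "In an attempt to determine whether rTMS impacts craving and pain by reducing depressive symptoms". The method is one clause: "we will also examine models that do and do not control for changes in depression scores". No lag between mood and outcome, mediation method, assumptions or sensitivity analysis is given. The covariates named as examples for the mixed models are all baseline values.

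The Schedule of Visits and Assessments fixes the timing:

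- **Depression.** "Patient Health Questionnaire Nine (PHQ9)(60): Self-Report measure of depressive symptoms" is marked at Baseline and at the 1 and 4 week follow-up, with nothing under Post. The analysis text does not name the depression scale, but this is the only one in the schedule with a post-baseline mark.
- **Craving.** "The three-item scale will also be administered at 1 and 4 week" follow-ups, without cue provocation.
- **Questionnaire pain (BPI and McGill).** "Administered daily during the acute phase of the study and at both follow-up visits".
- **Opiate use.** "Time Line Follow Back (61): See above" is marked at Baseline and at the 1 and 4 week follow-up.
- **Main aims.** For Aim 2 the schedule gives "Primary outcome: Change score in thermal pain threshold and pain tolerance". This testing and the cue-provoked craving of Aim 1 are marked at Baseline and Post only.

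The Sample Size Justification adds that estimates from both unadjusted and adjusted analyses will feed the design of a larger trial. It does not say whether the mood-adjusted models are among them.

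**The concern.** At weeks 1 and 4, depression and outcome are recorded at the same visit, so neither comes first in time. A smaller rTMS coefficient after adjusting for depression change fits three accounts:

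1. rTMS improves mood, and better mood lowers craving or pain.
2. rTMS lowers craving or pain, and mood follows.
3. rTMS reduces relapse, and relapse drives both mood and the outcome.

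Only the first is what the analysis is meant to detect. The others come from the protocol's own expectations: its Exploratory Aim hypothesizes more abstinence on active rTMS, and its statement of potential benefits lists craving, pain and depression together.

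At stake is whether rTMS appears to have its own anti-craving and anti-pain effect or only an antidepressant one. If a mood-adjusted coefficient were carried into the next trial's sample size, it could also understate the effect to be detected.

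**Working it through.** **The plan's own figure.** The documents give no number for the depression-adjusted models. The nearest stated figure is power above 80% for d = 1.0, two-sided alpha 0.05, with 20 per arm recruited and at least 32 completers (16 per arm if even). By the normal approximation, power = Φ(d√(n/2) − 1.96):

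- n = 16: Φ(2.828 − 1.96) = 80.7% (noncentral t: 78.1%)
- n = 20: Φ(3.162 − 1.96) = 88.5% (noncentral t: 86.9%)

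The figure reproduces, within 2 points for the t version at 16 per arm, and is not in dispute. I use d = 1.0 below only as a scale; the shares do not depend on it.

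**What adjustment does.** Let X be the arm, Y the reduction in craving or pain, and M the reduction in PHQ-9. In a linear model,

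unadjusted coefficient − adjusted coefficient = a × s,

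where a is the arm effect on M and s is the within-arm slope of Y on M. Both must be non-zero for the coefficient to move.

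**Mood purely a result of the outcome.** Take Y = τX + e and M = rY + √(1 − r²)u, with e and u of unit variance, so r is the within-arm correlation. Then a = rτ and s = r. The adjusted coefficient is τ(1 − r²) and the share falsely credited to mood is r². The documents give no r, so a range is assumed:

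| r | Adjusted effect, τ = 1.0 | Share credited to mood |
|---|---|---|
| 0.3 | 0.91 | 9% |
| 0.5 | 0.75 | 25% |
| 0.7 | 0.51 | 49% |

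Simulation with 1,000,000 records per setting gave the same shares.

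**Mood a true mediator.** Take M = rX + u and Y = (1 − r²)X + rM + √(1 − r²)w. The total effect is (1 − r²) + r² = 1 and the adjusted effect is 1 − r². Arm differences, variances and within-arm correlation all match the previous model with τ = 1. The shares are again 9%, 25% and 49%, so no sample size separates the two accounts.

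**A shared cause that rTMS changes (relapse).** Suppose rTMS shifts relapse by δ, and relapse loads equally (λ) on Y and M, with no other rTMS effect and no role for mood. Then a = λδ, the total effect on Y is λδ, and s = r = λ². The false share is λδ·r / λδ = r: 30%, 50% and 70% at the same three values. Equal loading is an assumption.

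**A shared cause that rTMS does not change.** Here a = 0, so nothing shrinks. With a true effect of 0.65 and r = 0.5, simulation gave 0.65 both unadjusted and adjusted. Likewise, if rTMS has no effect on Y and mood only follows Y, adjustment changes nothing on average.

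**At this trial's size.** In 10,000 simulated trials of 16 per arm (d = 1.0, mood purely a result), the coefficient moved toward zero in 78%, 92% and 97% of runs at r = 0.3, 0.5 and 0.7. At r = 0.5 the middle 95% of the changes ran from −0.10 to 0.72, so one trial can miss or exaggerate the shift.

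**Whether a lag repairs it.** Use week-1 PHQ-9 change for the week-4 outcome, with outcome correlation ρ between weeks 1 and 4. If mood is purely a result, the false share is ρr². At an assumed ρ = 0.6 this is 0.6 × 0.09 = 5%, 0.6 × 0.25 = 15% and 0.6 × 0.49 = 29%. Adding the week-1 outcome brings the PHQ-9 coefficient to about 0 in that model. But if mood truly carries the whole effect and has done so by week 1, the week-1 outcome absorbs it and the lagged product is also about 0.

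**The case against.** The other side has several fair points.

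- **Correlation is not enough.** A reader might infer that mediation will be reported whenever mood and outcome correlate within arm. The identity above does not support that: the arms must also differ on PHQ-9 change, and relapse or withdrawal matters only if rTMS alters it. This stands and limits the point.
- **Not identified is not the same as wrong.** A reader might infer that the mechanism conclusion must be false. If mood does mediate, the comparison points the right way. What fails is the ability to tell.
- **Scope.** The main outcomes of both aims are taken at Post, where no PHQ-9 is marked. Any depression change used for them would be measured after the outcome, which is a separate and worse ordering problem that this point does not repair. The point covers uncued craving, BPI and McGill at follow-up, which the General Overview calls exploratory. The text also does not say which PHQ-9 change enters the model, so a lag is possible but unplanned.
- **Effect size.** It is tempting to apply the d = 0.65 quoted for Aim 2. It comes from a single-session study whose pain result was thermal, and thermal pain is not measured at weeks 1 or 4. It does not size the follow-up outcomes.
- **Weight.** The analysis is described as an attempt, in an exploratory project, with no decision rule or mediation percentage. That tempers the seriousness, but the stated purpose is still causal and this comparison is the only method offered for it.

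**Conclusion.** The concern holds in limited form. For uncued craving, BPI and McGill at weeks 1 and 4, the with/without comparison cannot separate mediation by mood from mood following the outcome, or from a relapse effect of rTMS on both. Under pure reverse causation the falsely credited share is r²: 9% to 49% for assumed r of 0.3 to 0.7. That rests on a linear model, a non-zero rTMS effect on the outcome, and a PHQ-9 that responds to the outcome so that the arms differ on it. The shares are expected values, and a single trial of 32 to 40 participants may not show them.

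A reader might infer that the trial's efficacy result is compromised. It is not: the unadjusted treatment comparison does not use depression change. Nor do the documents commit the sponsor to designing the next trial from mood-adjusted estimates; they only leave that open. The change is worth making because it alters what the trial may conclude about mechanism at almost no cost.

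**What to change.** In the Statistical Analysis text of section D, state that models adjusting for depression change measured at the same visit as the outcome:

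1. are associational;
2. will not be read as evidence that rTMS acts, or does not act, through mood;
3. will not supply the treatment-effect estimate used to design the next trial.

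A lagged analysis (PHQ-9 change from Baseline to week 1, outcome at week 4) may be added, but only as an exploratory sensitivity analysis and shown both with and without the week-1 outcome. Without it, false mediation remains; with it, true mediation complete by week 1 is missed. Neither version should replace the planned comparison as a test of mechanism.

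The cost is a few sentences of SAP wording and no new data. The trial gives up a firm statement on mechanism. Any lagged estimate will have a wide interval at 32 to 40 participants: one of its ingredients, the arm difference in PHQ-9 change, already has a 95% half-width of 1.96√(2/20) = 0.62 to 1.96√(2/16) = 0.69 SD.

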To date there has been limited work examining the effect of rTMS on craving or pain in individuals with OUD. Drawing from the published literature suggesting that excitatory rTMS applied to the DLPFC can reduce both pain and craving, our group completed a preliminary sham-controlled crossover study in prescription OUD patients with chronic pain. Our data suggest that a single session of excitatory DLPFC rTMS *acutely* decreased opiate cue induced craving and thermal pain sensitivity in this group. The promising results from our single session trial parallel the single session results found in nicotine and cocaine use disordered populations

which subsequently translated into positive multiple session clinical trials. As such, it follows that a trial utilizing multiple sessions of rTMS in OUD patients may yield positive results.

The goal of this proposal is to investigate whether multiple sessions of rTMS applied to the DLPFC result in decreased craving (Aim 1) and pain (Aim 2) in treatment-seeking opiate users with or without chronic pain, who are currently hospitalized for opiate detoxification. Additionally, we will follow participants for four weeks to determine if treated participants have a higher rate of abstinence than un-treated participants (Exploratory Aim). These aims will be addressed through a double-blind, randomized, sham-controlled study. 40 participants (20/group) admitted to an inpatient community treatment facility for opiate detoxification will be given 18 sessions of either active or sham rTMS applied to the DLPFC, in an accelerated fashion over three days (6-sessions each day).

Aim 1: Determine if a course of excitatory rTMS applied to the DLPFC results in reduced cue-induced craving. We hypothesize that patients receiving active rTMS will have a greater reduction in cue induced craving (post-treatment vs. pre-treatment) as compared to those receiving sham rTMS. Cue craving will be assessed using a standardized measure (21) during a validated opiate cue paradigm (22).

Aim 2: Determine if a course of excitatory rTMS applied to the DLPFC results in decreased pain. We hypothesize that patients receiving active rTMS will have a greater reduction in pain (post-treatment vs. pretreatment) as compared to those receiving sham rTMS. Pain will be assessed using clinically relevant subjective measures (23, 24). We will also assess pain using a validated quantitative sensory testing paradigm.

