Integration of Study Procedures Into Inpatient Care: During inpatient care, standard treatment includes a combination of pharmacotherapy, psychotherapy, and social work interventions. Pharmacotherapy consists of detoxification from opiates (using a standardized protocol), and the use of medications to treat co-occurring conditions. During detoxification patients are assessed twice daily using the Clinical Opiate Withdrawal Scale (COWS) (57), and then undergo either a standardized buprenorphine taper (8mg x 2 days, 4mg x 3 days), or a standardized methadone taper (30, 25, 20, 15, 10, 5). Induction using either medication occurs at approximately 10am on the first morning of admission. On each of the following four days, medication is given at approximately 10am, and patients are discharged on the final day of their taper following their final dose of

medication. Currently there are no regular group therapy sessions, and regular meetings with individual therapists, social workers, and prescribers are less than 60 minutes in duration each.

The study has been designed specifically to not interfere with any aspect of the normal unit operations. One of the qualified study members will meet with interested patients once they are stable on buprenorphine/methadone, and no longer in acute withdrawal, subsequently the study will not interfere with the initiation of buprenorphine/methadone. Patients who would like to participate in the study, will be consented, enrolled, and will complete baseline assessments prior to starting treatment. The opiate cue craving paradigm, inhibitory control/delayed discounting paradigm, and the quantitative sensory testing will be completed on the morning after being induced on buprenorphine/methadone (before any rTMS), and the morning of the last dose of buprenorphine/methadone on the discharge day (after all rTMS has been delivered). Subsequently assessments will occur at the same time of day, and prior to patients taking buprenorphine/methadone, without disrupting the normal dispensing of medications (which is approximately 10am). Six 15 minute treatments will be delivered each of the next three days with approximately 30 minutes in between each treatment. Given that all standard treatment meetings (see above) occur in windows of less than 60 minutes, and rTMS will be delivered on the same floor as detoxification, study treatment will not interfere with any of the standard of care interventions participants receive.

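### Modifiers of the rTMS effect are sought in the active arm alone, which shows who improves, not who benefits from rTMS over sham

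*Combined protocol and SAP*

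**What the plan says.** All of the following is in Section D, under Data Management and Statistical Analysis, unless stated otherwise.

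- **Main model.** Change over time is compared between active and sham rTMS with general linear mixed models (GLMMs), "while controlling for relevant baseline covariates (e.g. baseline craving, morphine equivalents, withdrawal"). No characteristic-by-treatment term is stated for these covariates.
- **Differential effects.** "Primary outcomes will also be analyzed for evidence of differential treatment effects in subgroups determined by gender, race, and ethnicity". No other characteristic is named.
- **Characteristics.** "Post-hoc exploratory analyses using GLMMs within the active rTMS group will address whether specific characteristics". The examples listed are demographics and the three covariates of the main model, and the stated purpose is to find those that "are associated with a better treatment effect".
- **Reporting.** The next sentence reads: "The subgroup-specific treatment effects and corresponding confidence intervals will be constructed and will be interpreted in terms of their clinical, rather than statistical, significance".
- **Timing.** Integration of Study Procedures Into Inpatient Care says that the cue-craving and sensory tests "will be completed on the morning after being induced on buprenorphine/methadone (before any rTMS"), and again on the morning of the last taper dose.
- **Outcome.** Aim 1 hypothesises a "greater reduction in cue induced craving (post-treatment vs. pre-treatment") in the active arm than in the sham arm.

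**The concern.** The question asked is for whom rTMS works better. That needs the active-minus-sham difference to be compared across levels of the characteristic. The planned model relates the characteristic to change in treated patients only.

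This trial is exposed to that gap for two reasons. Every participant is in a medication taper for the whole interval between the two tests, so withdrawal severity, morphine equivalents and craving at entry may well predict change in either arm. Baseline craving is also one of the two terms in the Aim 1 change score, so regression to the mean ties the two together with no treatment effect at all.

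Patients who would have improved on sham could therefore be reported as those who gain more from rTMS. The plan says its model estimates will feed the design of a larger trial, which could then select or stratify on the wrong patients. The error can also run the other way: a true modifier may show no association within the active arm.

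**Working it through.** **Inputs from the documents.** 40 randomised, 20 per arm. Fewer than 20% lost, so at least 40 × 0.8 = 32 completers, or 16 per arm if losses are even. Two-sided alpha 0.05.

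**The plan's own figure.** It claims more than 80% power at d = 1.0. With 16 per arm, the normal approximation gives Φ(1.0 × √(16/2) − 1.96) = Φ(0.868) = 80.7%; the noncentral t gives 78.1%. The figure reproduces on the first method and is not disputed here.

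**What each model estimates.** Let β_A and β_S be the slopes of change on the characteristic in the active and sham arms. Effect modification is β_A − β_S. The active-only model estimates β_A = β_S + (β_A − β_S). With no modification it still estimates β_S, which is non-zero for any prognostic characteristic.

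**Baseline craving against craving change.** Assumptions: baseline SD 1, post-treatment SD k, pre-post correlation ρ, no rTMS effect. A uniform effect would leave the slope the same.

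- Slope = ρk − 1
- Correlation = (ρk − 1)/√(1 + k² − 2ρk)

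At k = 1 the correlation reduces to −√((1 − ρ)/2). For example, ρ = 0.5 gives −√0.25 = −0.50. Higher baseline craving then goes with a larger reduction. The share of active-only analyses with p<0.05 (600,000 simulated active arms per cell) was:

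| ρ (k = 1) | Correlation | n = 16 | n = 20 |
|---|---|---|---|
| 0.3 | −0.59 | 72% | 82% |
| 0.5 | −0.50 | 53% | 64% |
| 0.7 | −0.39 | 33% | 40% |
| 0.8 | −0.32 | 23% | 28% |
| 0.9 | −0.22 | 13% | 16% |

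The SD ratio matters, here at n = 16:

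- k = 0.8 gives 73% to 91%.
- k = 1.25 gives 46/24/8/5/13% across the same ρ values. At ρ = 0.8 the slope is 0.8 × 1.25 − 1 = 0, so there is no excess. At ρ = 0.9 it is +0.125, so the sign reverses.

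**Other characteristics, such as withdrawal.** Assume the same correlation with change in both arms and no modification (40,000 simulations per cell):

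| Correlation with change | n = 16 | n = 20 |
|---|---|---|
| 0.2 | 12% | 14% |
| 0.3 | 21% | 25% |
| 0.4 | 35% | 42% |

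At a correlation of 0.1 the rate at n = 16 is about 6%, so a barely prognostic characteristic does little harm.

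**Two-arm interaction test.** In the same settings (40,000 trials per cell, slope difference tested on 2n − 4 degrees of freedom) it rejects in 4.7% to 5.3%.

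**The reverse error.** Take a true modifier with slope −0.5 in sham and 0 in active. The active-only model flags it in about 5% of trials. The interaction test flags it in 31% at 16 per arm and 38% at 20 per arm (5,000 runs).

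**The case against.** - **The analysis carries little weight.** It is called post-hoc and exploratory, has no significance rule, and supports no aim or sample-size decision. That stands and limits the consequence. It does not alter the quantity estimated, and a clinical reading of the wrong slope is still a reading of the wrong slope.
- **The sentence on subgroup-specific effects could cover the listed characteristics.** It is loosely worded. But it names no further subgroup, and effects against sham cannot come from a model without sham patients. The fair statement is that no differential-effect analysis is stated for these characteristics.
- **The size rests on assumptions.** This also stands. The p<0.05 flag is not the plan's rule, and at n = 16 the baseline-craving rates run from 5% to 91%. The largest rates apply only to baseline craving paired with craving change. The plan does not say whether the response is change or the post-treatment score. With the post-treatment score the null slope is ρk, usually positive, so high baseline craving would look like a worse result. Neither slope is a treatment effect.
- **The trial is too small for interactions.** Precision is indeed poor. That is a reason to report estimates with wide intervals, not to call a within-arm slope a treatment effect.
- **Looking for predictors of response in treated patients is a legitimate pilot aim.** Agreed, provided it is described as that.

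**Conclusion.** The concern holds: followed exactly as written, the analysis gives the wrong quantity for the question it names. It identifies who improves during rTMS and the taper, not who gains more from rTMS than from sham. Apart from gender, race and ethnicity, no characteristic has a stated analysis of differential effect.

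The structural point needs no numerical assumption. How often it would mislead does: it depends on the pre-post correlation, the SD ratio and the prognostic strength of each characteristic, none of which the documents give. Across most of the ranges tried, the active-only model flags purely prognostic characteristics well above 5%; in a few settings there is little or no excess. The plan should be changed, but the main between-arm comparisons are not in question.

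**What to change.** Fit these models in both arms. Add a characteristic-by-treatment (by time) term to the GLMM that already adjusts for baseline craving, morphine equivalents and withdrawal, and do the same for any other demographic of interest. Report the interaction estimate with its 95% confidence interval. If within-active associations are also shown, call them predictors of outcome. That relabelling alone would remove the misreading, but it would leave the question about treatment effect unanswered.

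The cost is one or two sentences; the sham patients have the same baseline measures. The price is imprecision:

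| Quantity | 16 per arm | 20 per arm |
|---|---|---|
| Power, slope difference of 0.5 residual SD per baseline SD | about 25% | about 31% |
| Power, slope difference of 0.8 | about 53% | about 64% |
| 95% CI half-width, same unit | about 0.77 | about 0.68 |

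For a characteristic that splits patients evenly, the standard error of the interaction is √(8/n) SD. The half-width is 2.048 × 0.707 = 1.45 SD at 16 per arm and 2.028 × 0.632 = 1.28 SD at 20 per arm. The results should be read as estimates for planning, not as tests.

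### The 0.3 SD precision given for the overall effect size is less than half the unadjusted active-versus-sham half-width of 0.64 to 0.72 SD

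*Combined protocol and SAP*

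**What the plan says.** The Sample Size Justification (Section D, Data Management and Statistical Analysis) states: "A total of n=40 participants (n=20 per arm) will be recruited". On attrition it says "We anticipate that <20% of study participants will withdraw from the study or be lost to follow-up", so that "≥ n=32 participants are expected to complete the study". Two precision statements follow. Group-specific changes are to be estimated "with 95% confidence intervals extending ~0.5 standard deviation units". The next sentence, introduced as a parallel statement, says "the overall effect size confidence interval will likely extend only 0.3 standard deviation units". The same paragraph then claims more than 80% power for a Cohen's d of 1.0 at a two-sided alpha of 0.05.

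*Overall effect size* is not defined there. The Statistical Analysis text just before it says "changes over time will be compared between treatment groups (active rTMS vs. sham rTMS) using general linear mixed models (GLMMs" and that the "GLMMs will allow us to estimate group-specific changes over time and overall effect sizes", "while controlling for relevant baseline covariates". No correlation, R-squared or formula is given for either precision figure.

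**The concern.** The natural reading of an overall effect size, named beside but apart from the group-specific changes in models that compare the arms, is the active-versus-sham difference. On that reading the paragraph says the difference between two arms will be known more tightly (0.3 SD) than the change in either arm alone (0.5 SD). For an unadjusted comparison of independent arms with equal SDs this cannot be so: the variances add, and with equal arms the difference is about 1.4 times less precise than each arm.

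The stakes are interpretive. The plan concedes that the study may not be fully powered, offers precision of estimation as part of the case for 40 participants, and intends the estimates to inform a larger trial. A reader relying on 0.3 SD would expect a treatment estimate more than twice as precise as the unadjusted design delivers. For example, an observed d of 0.65, the plan's own pilot value for Aim 2, would have an unadjusted interval reaching about zero (0.65 − 0.64 = 0.01 at 20 per arm; 0.65 − 0.72 = −0.07 at 16 per arm).

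**Working it through.** **Inputs.** From the Sample Size Justification: 20 per arm recruited, at least 32 completers, 95% intervals, results in SD units. Assumed here: SD = 1 and equal in both arms; 32 completers split 16/16 unless stated.

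**Step 1: the plan's 0.5 SD for one arm.** Half-width = t(0.975, n−1)/√n.
- n = 20: 0.468
- n = 16: 0.533 (with z: 1.96/4 = 0.490)

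This reproduces about 0.5 and fixes the convention as a half-width. A full-width reading would need a half-width of 0.25, hence (1.96/0.25)² ≈ 61.5, or about 62 per arm.

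**Step 2: active minus sham, same convention, unadjusted.** Half-width = t(0.975, 2n−2) × √(2/n).
- n = 20: 2.024 × 0.316 = 0.640
- n = 16: 2.042 × 0.354 = 0.722
- 32 completers split unevenly, t(0.975, 30) × √(1/a + 1/b): 18/14 gives 0.728; 20/12 gives 0.746

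Ratios to the stated value: 0.640/0.3 = 2.1 and 0.722/0.3 = 2.4. As a cross-check from the plan's own figure, two arms each at ±0.5 give 0.5 × √2 = 0.71 for their difference.

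**Step 3: what 0.3 SD would require.**
- Sample size: t(0.975, 2n−2) × √(2/n) first falls to 0.3 or below at n = 87 per arm (0.299).
- Covariate adjustment, with half-width scaled by √(1−R²): R² = 1 − (0.3/0.640)² = 0.78 at 20 per arm; 1 − (0.3/0.722)² = 0.83 at 16 per arm.

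| Assumed R² | 20 per arm | 16 per arm | Multiple of 0.3 |
|---|---|---|---|
| 0 | 0.640 | 0.722 | 2.1 to 2.4 |
| 0.25 | 0.554 | 0.625 | 1.8 to 2.1 |
| 0.50 | 0.453 | 0.511 | 1.5 to 1.7 |

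**Step 4: consistency with the power sentence.** Power at d = 1.0 is 0.869 (t) or 0.885 (z) at 20 per arm, and 0.781 (t) or 0.807 (z) at 16 per arm, broadly in line with the claim. A half-width of 0.3 implies a standard error of 0.3/1.96 = 0.153. That would give power above 99.9% at d = 1.0, and 80% power already at d = (1.96 + 0.8416) × 0.153 ≈ 0.43. The two statements cannot describe the same contrast.

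**Step 5: where 0.3 may have come from.** Two nearby quantities lie close to it.
- Mean change pooled over both arms: z 1.96/√40 = 0.310 and 1.96/√32 = 0.346; t 0.320 and 0.361.
- Standard error of the difference, without its multiplier: √(2/20) = 0.316; √(2/16) = 0.354.

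**The case against.** The strongest reply is that the term is undefined and the calculation may be correct for something else. With z quantiles and 32 completers, the one-arm half-width is 0.490 and the pooled half-width is 0.346. These round to exactly the two printed values and use the completer count given just before them. On that view the number is right and only the label is poor. This is a plausible origin and it stands as an explanation. It does not rescue the sentence. A pooled change mixes active and sham participants and answers neither Aim 1 nor Aim 2, and the same paragraph goes on to use effect size for Cohen's d.

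A second reply is that covariate adjustment is planned and will narrow the interval. That is true, and the statement that a difference cannot be tighter than one arm's change applies only without adjustment. The printed figure is also rounded: if 0.3 covers anything below 0.35, the R-squared needed falls to about 0.70 to 0.77. That is still high, and the plan states no value.

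Third, the project is presented as exploratory, and the d = 1.0 power statement already signals limited precision. That supports a low grading but leaves the 0.3 uncorrected.

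**Conclusion.** The concern holds, as a minor point. Read as the active-versus-sham effect, the stated 0.3 SD should be 0.64 SD (20 per arm) to 0.72 SD (16 per arm) unadjusted, rising to about 0.75 SD if the 32 completers split 20/12. This rests on equal SDs in the arms and on the half-width convention that reproduces the plan's own 0.5. Any adjusted figure depends on an R-squared that the plan does not give. If the pooled mean change was meant, the fault is one of labelling, and the precision of the treatment effect is then missing from the justification.

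**What to change.** First state which quantity the 0.3 describes. If it is the active-versus-sham difference, define it so and replace the figure with about 0.64 SD (n = 40) to 0.72 SD (n = 32), unadjusted; alternatively, state the variance-reduction assumption that supports a smaller adjusted value. If it is the mean change pooled over both arms, label it as that and add the active-versus-sham figure beside it.

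The cost is a change of wording and a less favourable stated precision. Enrolment, endpoints, the analysis and the power sentence can stay as they are.
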